## **1.3 Risk/Benefits**

The major risks to the patient are related to the surgical procedure, prolonged intubation or initial reason for ICU admission (bleeding, infection, pain, etc). Participation in this protocol places the patient at minimal if any additional risk. Additional blood sampling with each ABG analysis or CBC represents only 0.1% of the estimated blood volume of a 15 kg child and a much smaller percentage in larger patients. The maximum additional volume removed for sampling in one subject (40 mL) represents approximately 3.4% of the estimated blood volume of a 15 kg child and a much smaller percentage in larger patients. It is expected that many subjects will have fewer than 10 blood samples ordered by the ICU care team that would be used for data collection in this study. The small additional volume needed for sampling will not adversely impact the patient. The additional blood volume removed for testing purposes will not be large enough to change transfusion decisions. Pulse oximeters are commonly utilized devices that are considered to be minimal risk. There is theoretically an extremely small risk of damage to the subject's fingers from the device including potential mild allergic reaction to sensor material and adhesives, temporary skin irritation or discomfort associated with exposure to the sensor.

There are no direct benefits to the subject from participation in this protocol. Possible future benefits to society or other patients may occur if the system is shown to be accurate enough to be used in place of invasive determination of Hb or PaO2 in critically ill adult patients.

**Safety parameters:** Case report forms will be analyzed quarterly by the internal review process of the Department of Anesthesiology/Critical Care Center Research Division. Any adverse events related to protocol participation will be reported to the IRB. In addition, all adverse events will be reported to the sponsor.

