## **4 SUBJECT SELECTION AND WITHDRAWAL**

### **4.1 Inclusion Criteria**

- Admitted into the SICU/8100, CTICU/7100, or NMCCS 8100 or 9100
- Aged 18 years or older
- Mechanically ventilated
- Arterial line placed
- Vigileo/Flotrac System being used for guidance of fluid management

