### 6.3 Sample Collection

Each patient enrolled in this trial will have Hb measured and recorded prior to data collection. SpHb data will be obtained continuously or via spot check in SICU/8100, CTICU/7100 or NMCCS 8100 or 9100. During spot checks, blood samples must be obtained simultaneously with noninvasive reading and will thus be coordinated. SpHb will be recorded with each blood draw sample. Additional blood sampling is necessary to validate the SpHb system. For patients over 15 kg weight, at each standard of care ABG sampling an additional 4 mL of blood will be collected for patients in the SICU/8100, CTICU/7100 or NMCCS 8100 or 9100 and sent for cell count and cyanomethemoglobin determination by Masimo laboratories. These additional samples will be obtained to a maximum of 10 ABG samples per patient, only when ordered by ICU team. Thus up to 40 mL total additional blood volume may be obtained in one subject. Blood samples will be inverted or rolled 10 times to ensure proper mixing to prevent micro clotting. Patients less than 15 kg will not have any additional blood sampling done at the time of ABG analysis. All decisions regarding fluid management and the need for transfusion will be at the discretion of the attending physicians caring for the patient and will be based on the results of the clinical status and Hb measured by CBC as is customary for transfusion. The time of the CBC draw and corresponding blood samples will be noted as part of the data collection for validation of the system.

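### Does the 0.1% per-draw blood-loss figure in Section 1.3, which conflicts with the protocol's own 4 mL draw, call for a change to the plan?

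*Combined protocol and SAP*

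**What the plan says.** Section 1.3 (Risk/Benefits) gives two percentages for one reference subject, a child of 15 kg. For a single draw: "Additional blood sampling with each ABG analysis or CBC represents only 0.1% of the estimated blood volume of a 15 kg child". For the whole study: "The maximum additional volume removed for sampling in one subject (40 mL) represents approximately 3.4% of the estimated blood volume of a 15 kg child". After each figure it adds that the share is much lower in heavier patients. The same section concludes that taking part adds little or no risk, and that the extra sampling will not alter transfusion decisions.

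Section 6.3 (Sample Collection) gives the volumes for patients above 15 kg: "at each standard of care ABG sampling an additional 4 mL of blood will be collected". It caps the number of draws: "These additional samples will be obtained to a maximum of 10 ABG samples per patient, only when ordered by ICU team". It then states the total: "Thus up to 40 mL total additional blood volume may be obtained in one subject". Patients below 15 kg have no extra blood taken.

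Section 4.1 (Inclusion Criteria) limits enrolment to adults: "Aged 18 years or older".

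**The concern.** Section 1.3 contradicts itself in consecutive sentences. Ten draws at 0.1% each make 1.0%, yet the ten-draw total is given as 3.4%. The per-draw number is the one that looks wrong, and it errs on the reassuring side.

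These two percentages are the only figures that Section 1.3 gives for the burden of blood sampling. They stand beside its statements on low risk and on transfusion decisions, in a study that Section 2 describes as enrolling anemic patients. If an ethics board or investigator judged the burden from the per-draw figure, an understatement of more than threefold could matter. The reference subject adds to the doubt, because an adults-only study describes its sampling risk for a child and keeps a 15 kg sampling threshold. It is fair to ask whether the risk to the people actually enrolled has been worked out at all.

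**Working it through.** **Inputs.** 4 mL per draw, at most 10 draws and 40 mL in total (Section 6.3); 0.1% per draw and 3.4% for 40 mL, both for 15 kg (Section 1.3). The documents give no blood volume per kilogram, so it is derived below from the 3.4% and then varied.

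**Step 1: the figures that agree.**
- Total volume: 10 × 4 mL = 40 mL, as stated in both sections.
- Blood volume implied by 40 mL = 3.4%: 40 / 0.034 = 1176 mL, and 1176 / 15 = 78.4 mL/kg.
- If 3.4% is rounded from anywhere between 3.35% and 3.45%, the implied value is 79.6 to 77.3 mL/kg.

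**Step 2: the figure that does not agree.**
- Share per draw: 4 / 1176 = 0.34%, which is also 3.4% / 10.
- Ratio to the printed figure: 0.34 / 0.1 = 3.4.
- Draws needed to reach 3.4% at 0.1% each: 3.4 / 0.1 = 34, against a maximum of 10.
- Volume that would be 0.1%: 0.001 × 1176 = 1.2 mL, which the protocol does not give as a draw volume.

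**Step 3: can a benign reading rescue 0.1%?**
- For 4 mL to be exactly 0.1%, blood volume must be 4 / 0.001 = 4000 mL, or 267 mL/kg at 15 kg.
- If 0.1% is rounded down from just under 0.15%: 4 / 0.0015 = 2667 mL, or 178 mL/kg.
- At an assumed 65 to 85 mL/kg, 4 mL is 0.41% to 0.31% at 15 kg.

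None of these readings works. The number is wrong for the subject it names.

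**Step 4: what it means for eligible subjects.** The implied 78.4 mL/kg is assumed to hold for adults.

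| Weight | Blood volume | One 4 mL draw | Maximum 40 mL |
|---|---|---|---|
| 50 kg | 3922 mL | 0.10% | 1.0% |
| 70 kg | 5490 mL | 0.07% | 0.7% |
| 100 kg | 7843 mL | 0.05% | 0.5% |

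On this assumption 4 mL equals 0.1% at about 4000 / 78.4 = 51 kg. At a lower assumed 65 mL/kg, the 50 kg figures are 4 / 3250 = 0.12% per draw and 40 / 3250 = 1.2% in total, and the 0.1% point moves to 4000 / 65 = 62 kg.

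**Step 5: what uses the 0.1%.** The sampling rule in Section 6.3 is set in millilitres and number of draws, not as a percentage. Eligibility (Sections 4.1 and 4.2), data analysis (Section 6.5) and adverse event reporting (Section 7.3) do not refer to the figure. Under Section 6.3, transfusion remains the treating physicians' decision.

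**The case for a change.** The strongest case for acting is that risk text is written to be relied on. The error favours the study, and the percentages given are for a child, not for the anemic adults being sampled. Section 1.1 itself grants that repeated laboratory sampling can occasionally cause meaningful blood loss. The error also touches the adult reassurance. Read literally, heavier patients should lose much less than 0.1% per draw. That fails for lighter adults: about 0.10% at 50 kg on the implied blood volume, and 0.12% at an assumed 65 mL/kg. Correcting the text would cost almost nothing.

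Part of this stands. The number is wrong, the comparison with heavier patients does not hold against 0.1% for lighter adults, and the 15 kg references are leftover text that does not fit adults-only eligibility.

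The consequence does not follow. Measured against the true child figure of 0.34%, the adult shares of 0.05% to 0.12% are indeed much smaller, so the sense of the sentence survives. Blood-loss risk depends on the total, and the total is stated correctly in the very next sentence: 40 mL, which "represents approximately 3.4% of the estimated blood volume of a 15 kg child". A reader of Section 1.3 therefore sees a worst case larger than any adult in the table would face. The 15 kg sampling threshold has no practical effect in adults. Whether the figure was repeated in other ethics documents cannot be judged from the text available.

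**Conclusion.** This is a clerical slip, and no change to the plan follows. The per-draw percentage in Section 1.3 should read about 0.34% for a 15 kg child if the stated volumes hold. The printed 0.1% is 3.4-fold too low, a result that needs only the protocol's own figures.

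The error concerns a subject who cannot be enrolled. For adults of 50 to 100 kg, one draw is about 0.10% to 0.05% of blood volume and the 40 mL maximum about 1.0% to 0.5%, assuming the implied 78.4 mL/kg applies to them. At an assumed 65 mL/kg the 50 kg figures rise only to 0.12% and 1.2%. The limits that protect subjects (4 mL, ten draws, 40 mL) agree wherever they appear. Correcting the number would alter no procedure, eligibility rule, safety rule, analysis or conclusion. The percentage and the leftover 15 kg wording can be tidied whenever the text is next edited, but nothing in the trial depends on it.

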## **2 STUDY DESIGN**

This is a sponsored, prospective, nonrandomized, sequential data collection study to be performed in anemic adult patients who are admitted into the Surgical Intensive Care Unit (SICU/8100), Cardiothoracic Intensive Care Unit (CTICU/7100) or Neuro-Multidisciplinary Critical Care Services (NMCCS 8100 or 9100). Noninvasive pulse oximetry-determined SpHb will be compared to ABG co-oximetry and research lab equipment-determined Hb values, Oxygen Reserve Index (ORI) will be correlated with paO2 via ABG, PVI and acoustic waveform data will be compared to the arterial waveform extracted SVV or PPV values. The study goal is to establish the correlation of Hb values determined by the SpHb system with Hb as measured by other validated devices, use ORI to correlate with paO2 in the moderate hyperoxic regions and correlation of PVI with SVV or PPV values.

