### **4.2 Exclusion Criteria**

- Pregnancy
- Prisoner status
- Extreme hemodynamic instability
- Multiple vasopressors in use with questionable peripheral blood flow
- Lack of appropriate sites for sensor placement
- Patient or patient's legal representative refusal

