### **4.3 Subject Recruitment and Screening**

The SICU/8100, CTICU/7100 or NMCCS 8100 or 9100 patient census will be screened by the research team to identify the potential candidates. There will potentially be up to 600 patients participating at Loma Linda University in this study.

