### 6.2 Study Duration

Patients admitted directly into SICU/8100, CTICU/7100 or NMCCS 8100 or 9100 may be monitored for up to three days.

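### In the text available, Sections 2 and 6.5 assess Hb by correlation alone, which cannot reveal a constant offset in SpHb

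*Combined protocol and SAP*

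**What the plan says.** **Statistic.** Section 2 announces a comparison without naming a measure: "Noninvasive pulse oximetry-determined SpHb will be compared to ABG co-oximetry and research lab equipment-determined Hb values". It then gives the aim: "The study goal is to establish the correlation of Hb values determined by the SpHb system with Hb as measured by other validated devices". Section 6.5 also plans correlation, between *changing* Hb concentrations from three methods and spectral absorbance. No bias, error measure, limits of agreement or acceptance limit for Hb appears in the text available. Section 3 was not available, so nothing is said here about its content.

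**Purpose.** Section 6.3 presents the additional sampling as needed for validation of SpHb: 4 mL at each of up to 10 ABG draws, or 40 mL per patient.

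**Sensors.** Section 6.1 allows up to eight noninvasive sensors per patient at different body sites. Section 5 includes prototypes among them.

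**Population.** Section 2 calls the study a "sequential data collection study to be performed in anemic adult patients who are admitted into the Surgical Intensive Care Unit". The five inclusion criteria in 4.1 end with "Vigileo/Flotrac System being used for guidance of fluid management", and the six exclusion criteria in 4.2 include "Extreme hemodynamic instability". Neither list has an Hb limit or a definition of anemia. Section 6.3 says "Each patient enrolled in this trial will have Hb measured and recorded prior to data collection", but no entry decision depends on that value. On size, 4.3 says only "There will potentially be up to 600 patients participating", and under 6.2 patients "may be monitored for up to three days".

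**The concern.** Correlation measures how closely two readings follow a straight line. It does not measure whether they agree. If SpHb reads high by the same amount in every patient, r is exactly what it would be for an unbiased device. A study following 6.5 as written could therefore report a high r for a device with a material offset, and a reader could take that as validation.

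The value of r also rises with the spread of Hb in the patients enrolled. Entry does not control that spread, so part of the result would reflect who happened to be admitted. This is where the unmatched word *anemic* touches the statistics, but it is the lesser issue.

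**Working it through.** **Inputs.** The documents give no Hb SD, device error, target correlation or margin, and 4.3 gives no derivation for 600. There is thus no figure of the plan's own to reproduce. All inputs below are assumptions: Hb mean 10 and SD 2.0 g/dl, device error SD 1.0 g/dl, error independent of Hb, reference free of error.

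**1. Constant offset.** Write SpHb = Hb + b + error.
- r = SD(Hb) / √(SD(Hb)² + SD(error)²) = 2.0 / √(4 + 1) = 0.894. The offset b does not enter.
- RMSE = √(b² + 1.0²), which is 1.00 at b = 0 and √2 = 1.41 at b = 1.0 g/dl.
- 95% limits of agreement = b ± 1.96 × 1.0, which are −1.96 to +1.96 at b = 0 and −0.96 to +2.96 at b = 1.0.

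If *changing* in 6.5 means within-patient change, b cancels: (Hb₂ + b) − (Hb₁ + b) = Hb₂ − Hb₁. The offset is missed there too.

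**2. Hb mix enrolled.** Let entry Hb and paired Hb be bivariate normal with correlation ρ, and restrict entry to Hb below a cut c. The variance of paired Hb becomes 4 × (1 − ρ²(1 − k)), where k is the ratio of restricted to unrestricted entry variance. For c = 10, the mean, k = 1 − 2/π = 0.363.

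| Entry | ρ = 1.0 | ρ = 0.9 | ρ = 0.7 |
|---|---|---|---|
| Unrestricted | 0.894 | 0.894 | 0.894 |
| Below 10 g/dl | 0.770 | 0.812 | 0.856 |
| Below 12 g/dl | 0.846 | 0.858 | 0.875 |

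For example, at c = 10 and ρ = 0.9 the variance is 4 × (1 − 0.81 × 0.637) = 1.94, and r = √(1.94 / 2.94) = 0.81. Over Hb mean 9.5 to 11, Hb SD 1.5 to 2.0, error SD 0.8 to 1.5 and ρ 0.7 to 1.0, unrestricted entry raises r by 0.02 to 0.27 against the cut at 10 and by 0.01 to 0.12 against the cut at 12. The cuts only illustrate. They are not in the entry criteria and are not proposed.

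**3. Why results by Hb level are still needed.** Limits of agreement are free of the Hb mix only if error does not vary with Hb. If error SD were 10% of Hb, their half-width would be 2.00 g/dl overall, 1.66 to 1.77 in patients entering below 10 g/dl, and 2.20 to 2.28 in the rest (ρ 1.0 to 0.7).

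**4. Precision.** With difference SD 1.0, m pairs per patient and an intraclass correlation of 0.5, the 95% half-width for bias is 1.96 × √((1 + 0.5(m − 1)) / (n × m)).
- n = 600: 0.065 g/dl at m = 3 and 0.059 at m = 10.
- n = 150, an assumed subgroup size: 0.131 and 0.119.
- For each limit of agreement, from balanced one-way variance components: 0.102 and 0.087 at n = 600, 0.204 and 0.174 at n = 150.

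**The case against.** **Section 3.** A reader might infer that the plan contains no agreement analysis anywhere. The available text does not support that, because Section 3 was not seen. If it specifies one, 6.5 needs only to be brought into line.

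**Spectral absorbance.** Part of 6.5 can be read as signal or algorithm work: the study uses prototype sensors and captured wavelength data, and sponsor engineers do the analysis. Relating absorbance to Hb has no bias in g/dl. This stands, and that part of 6.5 is outside the point. It does not remove the Section 2 goal, which concerns Hb values.

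**Replacement of invasive Hb.** A reader might infer from 1.3 that the study sets out to show that SpHb can replace blood Hb. Section 1.3 offers this only as a conditional, possible future benefit. The stated validation purpose in 6.3 is the firmer ground.

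**Non-anemic patients.** A reader might infer that enrolling them invalidates the study. It does not: a wide Hb range is not in itself a flaw in a method comparison, and adding an Hb criterion would not repair the statistic. The effect on r runs from negligible to material depending on assumed cuts and SDs.

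**Agreement statistics alone.** Without an acceptance limit, they would not show adequate accuracy either. Pooling across sensors and sites could also mix different devices. Both objections stand and shape the fix.

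**Conclusion.** The point holds for the Section 2 goal and for the Hb comparison in 6.5, within the text available. That r ignores a constant offset is exact and needs no assumption. Its illustrated size (r 0.89 in both cases, RMSE 1.00 against 1.41 g/dl) rests on the assumed SDs and an offset of 1.0 g/dl. The dependence of r on Hb mix is secondary: about 0.01 to 0.27 under the assumptions shown. The gap between *anemic* in Section 2 and the entry criteria is a separate wording conflict.

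The change should be made before analysis. The data already planned can support the better analysis, but the measure and any acceptance limit carry weight only if chosen before the results are known.

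**What to change.** **Section 6.5.** Make the primary Hb analysis the difference, SpHb minus each reference Hb named in Section 2.
- Report bias, RMSE and 95% limits of agreement, each with an interval, separately by sensor model and site rather than pooled.
- Use a mixed model on the differences with a patient effect (limits = bias ± 1.96 × the root of between- plus within-patient variance) or a patient-level bootstrap. Allow for however many pairs each patient contributes: the cap of 10 in 6.3 covers only the additional research samples.
- If an accuracy or validation conclusion is to be drawn, the sponsor should fix an acceptance limit before analysis.
- Report the enrolled Hb distribution, and results by pre-collection Hb level from 6.3, with the levels fixed in advance. Each patient then falls in one group, and the paired reference is not reused for grouping.
- Correlation can stay as a secondary description.

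**Sections 2 and 4.1.** Reconcile *anemic* with the criteria, either by removing the word or by defining anemia and adding it to 4.1. The choice is the sponsor's.

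**Cost.** Protocol text and extra analysis, with no new data. Intervals widen within sensor or Hb groups, as step 4 shows. Hb can also drift out of its pre-collection group over three days. With Hb mean 10, SD 2.0 and ρ 0.9 to 0.7, 0.5 − arcsin(ρ)/π gives 14% to 25% of pairs above 10 g/dl among patients entering below it. If an Hb criterion is added instead, the eligible pool shrinks.

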**DORO0001 version 1**

It may be that continuous Hb assessment could allow more accurate titration of blood transfusion to maintain Hb levels in a target range. This may result in limiting the total number of units transfused to a patient, the amount of time a patient's Hb level is above or below the target range, and the amount of blood draws for Hb lab checks.

[REDACTED] This information can be characterized as the Oxygen Reserve Index (ORI). This index is presented on a unit-less scale between 0 and 1 that correlates with arterial oxygen concentrations between 100 and 200mmHg. This index is designed to supplement standard arterial hemoglobin saturation monitoring. (12) Preliminary studies have evaluated the relationship between ORI and paO2 in the general surgical population. (11) In addition, the ORI has been demonstrated to provide a clinically useful advanced warning of impending arterial hemoglobin desaturation in pediatric patients. (13) The relationship between ORI and standard saturation monitoring is characterized by this illustration from the above referenced whitepaper:

Oxygen Reserve Index (ORI) is an index measured noninvasively and continuously to provide an earlier indication of impending hypoxia by extending oxygen monitoring of pulse-oximetry to the moderate hyperoxic (100-200 mmHg) regions.

The device also has the capability to continuously measure the plethysmography variability index (PVI). PVI is calculated automatically and represents the variation in amplitude of the pulse oximeter waveform with respiration (22-24). PVI is analogous to stroke volume variation (SVV), which may be derived from arterial waveform, pulmonary artery catheter, esophageal Doppler, echocardiography or other device measured variations with respiration [REDACTED]

[REDACTED] Of course use of this device requires an arterial catheter be placed. Multiple studies have demonstrated that SVV is a valuable tool in predicting fluid responsiveness in mechanically ventilated patients. When SVV is elevated, patients are more likely to respond with increased stroke volume and cardiac output when fluid is administered. The threshold SVV of

---

**Validation of a pulse oximetry based hemoglobin measurement system. Comparison of plethysmographic variability index to standard methods of guiding fluid and transfusion management in the critically ill adult patients. Validation of Clinical Efficacy of ORI for supplemental oxygen titration.**

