### 6.5 Data Analysis

Statistical analyses will be performed using statistical analysis software to determine the correlation between changing hemoglobin concentrations determined by the 3 different methods and spectral absorbance. ORI data will also be analyzed to determine any correlation with PaO2 obtained by ABG. PVI data will be correlated to SVV. Outcome data will be analyzed for any relationships between the inciting event, blood loss and outcome markers to evaluate for any predictive value of inciting factors and any correlation between transfusion and fluid management variables on outcome.

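### The only ORI analysis in the visible text is a correlation with PaO2; whether or not pairs are limited to 100-200 mmHg, it does not show what PaO2 lies behind a displayed ORI

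*Combined protocol and SAP*

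**What the plan says.** ORI and PaO2 are linked in three statements of what will be done.

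- Section 2, design sentence: "Oxygen Reserve Index (ORI) will be correlated with paO 2 via ABG". No PaO2 range is given.
- Section 2, goal sentence, which follows directly: "use ORI to correlate with paO 2 in the moderate hyperoxic regions".
- Section 6.5: "ORI data will also be analyzed to determine any correlation with PaO 2 obtained by ABG". Again no range.

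Section 1.1 supplies the range behind the goal sentence. It describes ORI as "extending oxygen monitoring of pulse-oximetry to the moderate hyperoxic (100-200 mmHg) regions", and says of its scale: "This index is presented on a unit-less scale between 0 and 1 that correlates with arterial oxygen concentrations between 100 and 200mmHg".

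The ambition is larger than a correlation. The last sentence of the protocol title calls the study a validation of ORI's clinical efficacy for titrating supplemental oxygen. Section 1.3 foresees a system "accurate enough to be used in place of invasive determination of Hb or PaO 2 in critically ill adult patients".

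Section 4.1 asks that patients be "Mechanically ventilated" with an arterial line in place. Neither Section 4.1 nor Section 4.2 sets a PaO2 limit, so pairs below 100 mmHg can be expected.

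The visible text contains no ORI cut-off, predictive value, cross-tabulation or summary of PaO2 by ORI, and no rule for pairs outside 100-200 mmHg. The text between Sections 2 and 4 was not available and other parts are redacted, so these absences are claimed for the visible text only.

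**The concern.** Someone using the monitor sees ORI and has to infer PaO2. The question that matches the title is therefore what PaO2 values occur when ORI shows 0, an intermediate value, or 1. On the scale in Section 1.1, an ORI above 0 suggests a PaO2 above 100 mmHg. The reading that would falsely reassure is ORI above 0 with PaO2 below 100 mmHg.

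The plan can be read in two ways, and neither describes that reading. Restricting to PaO2 of 100-200 mmHg selects on the reference value and removes exactly those pairs. Keeping all pairs retains them but merges them into one coefficient, which also depends on how widely PaO2 is spread in the sample. At stake is whether the ORI result can support a statement about oxygen titration or about replacing invasive PaO2.

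**Working it through.** **No figure to reproduce.** The documents give no expected correlation, success threshold, error SD or PaO2 distribution for ORI. The ceiling of 600 patients in Section 4.3 comes with no derivation.

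**Step 1: the filter.** Call a pair discordant if ORI > 0 and PaO2 < 100. A filter of 100 ≤ PaO2 ≤ 200 leaves 0 discordant pairs whatever the device does. This needs no assumption about the device, only that the filter is applied.

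**Step 2: all pairs kept, random error only.** All inputs are assumed:

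- PaO2 is lognormal with log-SD 0.35 and median 90, 120 or 150 mmHg.
- ORI = (PaO2 + error − 100)/100, limited to 0-1, with symmetric error of SD 10, 20 or 40 mmHg.
- 400,000 pairs were simulated per setting.

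The quantity of interest is P(PaO2 < 100 | ORI > 0) = P(discordant) / P(ORI > 0).

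| Median PaO2 | Error SD | r, all pairs | Discordant, % of all pairs | % of ORI > 0 with PaO2 < 100 |
|---|---|---|---|---|
| 90 | 10 | 0.87 | 4.8 | 12.4 |
| 90 | 20 | 0.81 | 9.8 | 23.8 |
| 90 | 40 | 0.63 | 17.1 | 38.2 |
| 120 | 10 | 0.92 | 3.8 | 5.4 |
| 120 | 20 | 0.87 | 6.6 | 9.6 |
| 120 | 40 | 0.70 | 9.9 | 15.0 |
| 150 | 10 | 0.88 | 2.0 | 2.2 |
| 150 | 20 | 0.83 | 3.2 | 3.8 |
| 150 | 40 | 0.70 | 4.4 | 5.4 |

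The coefficient does not determine the share. An r of 0.87-0.88 goes with 12.4%, 9.6% or 2.2%. An r of 0.70 goes with 15.0% or 5.4%. The setting with r 0.87 and 12.4% has a higher r than the one with r 0.83 and 3.8%.

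**Step 3: an assumed fault below 100 mmHg.** ORI = (PaO2 − 100)/100 + noise of SD 0.2 + an offset of 0, 0.2 or 0.4 only where PaO2 < 100, limited to 0-1. The log-SD is again 0.35. These figures use 2,000,000 simulated pairs per setting.

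| Median PaO2 | r within 100-200 (any offset) | r, all pairs (offset 0 / 0.2 / 0.4) | % of ORI > 0 with PaO2 < 100 (offset 0 / 0.2 / 0.4) |
|---|---|---|---|
| 90 | 0.76 | 0.81 / 0.76 / 0.62 | 24 / 45 / 58 |
| 100 | 0.78 | 0.84 / 0.80 / 0.67 | 18 / 35 / 47 |
| 120 | 0.80 | 0.87 / 0.84 / 0.76 | 10 / 20 / 28 |

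At median 100 with no offset, the share is 0.091/0.515 = 18%. With offset 0.2 it is 0.232/0.656 = 35%.

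**Step 4: how far below 100.** At median 100 with no offset, about 82% of discordant pairs have PaO2 of 80 mmHg or more. With offset 0.4 that falls to 58%. As a share of all ORI > 0 readings, PaO2 below 80 mmHg rises from 3.1% to 10.6% and 19.7% across the three offsets. Boundary noise and large errors therefore look different in the PaO2 distribution, which a coefficient does not display.

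**The case against.** A reader might infer that Section 2 confines the analysis to hyperoxic pairs and discards the rest, so that the error cannot be seen. The documents do not support that. The phrase is a goal clause and may only describe where ORI is designed to respond. Two of the three statements carry no range, and no visible text excludes a pair by its PaO2. The filter is a possible reading, not a stated rule.

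A reader might also infer that the unrestricted correlation is insensitive and that a faulty index would still yield a favourable result. That goes too far. At median 100 and offset 0.4, all-range r falls from 0.84 to 0.67, so r² falls from 0.71 to 0.45. Only the 0.2 offset gives a small change. No success threshold is stated, so no favourable result is defined.

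The offset is an invented fault, and the constant in-range r follows automatically from adding error only outside the range. It shows the mechanism, not a likely effect in this study. Most no-offset discordance is near the boundary: under 0.2% of ORI > 0 readings have PaO2 below 60 mmHg at median 100. The documents do not call a PaO2 just under 100 mmHg unsafe, and no visible study procedure adjusts oxygen from ORI.

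All of this stands, but it leaves the narrower point intact. Step 2 uses no fault at all, and r still fails to identify the share.

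**Conclusion.** The point holds on both readings of the plan. With a PaO2 filter, the pairs that would show false reassurance are absent by construction. Without one, they are present, but a single coefficient reports neither their frequency nor their depth. Neither version supports a conclusion about oxygen titration or about use in place of invasive PaO2.

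The size cannot be taken from the documents. Under the random-error assumptions, 2.2% to 38.2% of ORI readings above 0 have PaO2 below 100 mmHg. Under the assumed offsets the range is 10% to 58%. These figures depend on the assumed PaO2 spread, the ORI error and a linear scale from 100 to 200 mmHg. The zero count under a filter does not.

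This should be changed, but it is a gap in the analysis and an ambiguity in wording, not evidence that the plan discards data or that ORI misreads.

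**What to change.** In Sections 2 and 6.5:

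1. State that every ORI-ABG pair is kept whatever its PaO2, so that the goal sentence, the design sentence and Section 6.5 agree.
2. Group pairs by displayed ORI: 0, between 0 and 1, and 1. For each group report the numbers of pairs and patients, the PaO2 distribution, and the shares below 100 and above 200 mmHg. The distribution separates near-boundary misreadings from large ones.
3. Use patient-clustered intervals, for example from a bootstrap that resamples patients. Section 6.3 allows up to 10 research samples per patient and Section 6.2 up to three days of monitoring, so repeated pairs are likely.
4. Keep the 100-200 mmHg correlation as a secondary description.

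The cost is a wording change and one extra table from pairs already collected, with no added patients, blood draws or devices. The downside for the sponsor is that the ORI result may look less favourable.
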